3.4. Multiple Comparisons

Due to study early termination and insufficient number of subjects enrolled, the hypothesis testings performed and correspondingly reported p-values for all the comparisons planned in this SAP will be nominal, and need to be interpreted with caution.

3.5. Missing Data and Outliers

3.5.1. Missing Data

In general, missing data will not be imputed unless methods for handling missing data are specified. Exceptions are presented in this document.

For missing last dosing date of study drug, imputation rules are described in Section 4.2.1. For partial date of initial PsA diagnosis, imputation rules are described in Section 5.2. The handling of missing or incomplete dates for AE onset is described in Section 7.1.5.2, and for prior and concomitant medications in Section 7.4. Imputation rules adopted in the efficacy analyses are specified in Section 6.

3.5.2. Outliers

Outliers will be identified during the data management and data analysis process, but no sensitivity analyses will be conducted. All data will be included in the data analysis.

3.6. Data Handling Conventions and Transformations

The following conventions will be used for the imputation of date of birth:

- Since only the year of birth is collected in the study, “01 July” will be imputed as the day and month of birth
- If year of birth is missing, then date of birth will not be imputed.

In general, age collected at Day 1 (in years) will be used for analyses and presented in listings. If age at Day 1 is not available for a subject, then age derived based on date of birth and the Day 1 visit date will be used instead. If an enrolled subject was not dosed with any study drug, the randomization date will be used instead of the Day 1 visit date. For screen failures, the date the first informed consent was signed will be used for the age derivation.

Non-PK data that are continuous in nature but are less than the lower limit of quantitation (LOQ) or above the upper LOQ will be imputed as follows:

- A value that is 1 unit less than the LOQ will be used to calculate descriptive statistics if the datum is reported in the form of “< x” (where x is considered the LOQ). For example, if the values are reported as < 50 and < 5.0, values of 49 and 4.9, respectively, will be used to calculate summary statistics. An exception to this rule is any value reported as < 1 or < 0.1, etc. For values reported as < 1 or < 0.1, a value of 0.9 or 0.09, respectively, will be used to calculate summary statistics.
- A value that is 1 unit above the LOQ will be used to calculate descriptive statistics if the datum is reported in the form of “> x” (where x is considered the LOQ). Values with decimal points will follow the same logic as above.
- The LOQ will be used to calculate descriptive statistics if the datum is reported in the form of “≤ x” or “≥ x” (where x is considered the LOQ).

3.7. Analysis Visit Windows

3.7.1. Definition of Study Day

The study consists of two study phases: Main Study phase and LTE phase. Main study is from screening through Week 16 Visit. The subjects who complete the Main Study and have not prematurely discontinued study drug will continue on to the LTE. For the subjects who continue on to LTE phase, Main Study phase is up to Week 16 visit date (inclusive); LTE phase is from Week 16 visit date + 1 forward (for subjects enrolled under PA 1 who stayed in Main Study beyond Week 16 Visit, refer to Section 3.7.2 for exception).

The first dose date of individual study drug will be calculated separately for each study drug (ie, filgotinib 200mg, filgotinib 100mg, adalimumab and PTMs) in a treatment group. Study Day 1 is defined as the first dose date of any study drug, which is the minimum of the first dose dates of individual study drugs in a treatment group.

The last dose date of individual study drug will be calculated separately for each study drug in a treatment group. The last dose date for an individual study drug will be the maximum end date on study drug administration CRF for the record where the “study drug was permanently withdrawn” flag is “Yes”. The last dose date of any study drug will be defined as the maximum of the last dose dates of individual study drugs in a treatment group.

Study day will be calculated from the Study Day 1 and derived as follows:

- For postdose study days: Assessment Date – Study Day 1 + 1
- For days prior to the first dose: Assessment Date – Study Day 1

For subjects who continue on to the LTE, the LTE Study Day 1 is defined as the first dose date of any study drug for LTE. The LTE Study Day will be calculated from the LTE Study Day 1 and derived as follows:

- For days post LTE Study Day 1: Assessment Date – LTE Study Day 1 + 1
- For days prior to the LTE Study Day 1: Assessment Date – LTE Study Day 1

3.7.2. Analysis Visit Windows

Subject visits might not occur on protocol-specified days. Therefore, for the purpose of analysis, observations will be assigned to analysis windows.

In general, the study baseline value will be the last nonmissing value on or prior to the first dose date of study drug.

For subjects who were re-randomized to LTE phase (placebo or adalimumab treated subjects), the re-randomized baseline will be the last nonmissing value obtained on or prior to the first dose date of any study drug for LTE.

For subjects enrolled under PA 1 who stayed in Main Study beyond Week 16 Visit, the analysis visit window will only be applied to the data up to Week 16 visit.

The analysis windows for joint count assessment, HAQ-DI including subject's pain assessment, Patient's Global Assessment of Disease Activity (PGADA), Patient's Global Assessment of Psoriatic Arthritis Pain Intensity (PGAPI), Physician's Global Assessment of Disease Activity (PhGADA), CRP, vital signs, weight, and safety laboratory data (lipid data excluded) are provided in [Table 3-1](#).

Table 3-1. Analysis Visit Windows for Joint Count Assessment, HAQ-DI, PGADA, PGAPI, PhGADA, CRP, Vital Signs, Weight, and Safety Laboratory Data (Lipid Data Excluded)

Analysis Visit	Nominal Study Day	Visit Window Study Day	
		Lower Limit	Upper Limit
Baseline	1	(none)	1
Week 2	15	2	22
Week 4	29	23	43
Week 8	57	44	71
Week 12	85	72	99
Week 16	113	100	Week 16 Visit Date – Study Day 1 + 1*
Analysis Visit	Nominal LTE Study Day	LTE Lower Limit	LTE Upper Limit
Week 18	15	2	22
Week 20	29	23	43
Week 24	57	44	71
Week 28	85	72	113
Week 36	141	114	183
Week 48	225	184	267
Week 60	309	268	351
Week 72	393	352	435
Week 84	477	436	519
Week 96	561	520	603
Week 108	645	604	687
Week 120	729	688	≥ 729

* For subjects who did not enter LTE phase, upper limit is “>= 113”; for subjects enrolled under PA1 who stayed in Main Study beyond Week 16, upper limit is 127.

The analysis windows for lipid data are provided in [Table 3-2](#):

Table 3-2. Analysis Visit Windows for Lipid Data

Analysis Visit	Nominal Study Day	Visit Window Study Day	
		Lower Limit	Upper Limit
Baseline	1	(none)	1
Week 16	113	2	Week 16 Visit Date – Study Day 1 + 1*
Analysis Visit	Nominal LTE Study Day	LTE Lower Limit	LTE Upper Limit
Week 48	225	2	393
Week 96	561	394	645
Week 120	729	646	≥ 729

* For subjects who did not enter LTE phase, upper limit is “>= 113”; for subjects enrolled under PA1 who stayed in Main Study beyond Week 16, upper limit is 141.

The analysis windows for PhGAP data are provided in [Table 3-3](#).

Table 3-3. Analysis Visit Windows for PhGAP Data

Analysis Visit	Nominal Study Day	Visit Window Study Day	
		Lower Limit	Upper Limit
Baseline	1	(none)	1
Week 2	15	2	22
Week 4	29	23	43
Week 8	57	44	71
Week 12	85	72	99
Week 16	113	100	Week 16 Visit Date– Study Day 1 + 1*
Analysis Visit	Nominal LTE Study Day	LTE Lower Limit	LTE Upper Limit
Week 18	15	2	22
Week 20	29	23	43
Week 24	57	44	71
Week 28	85	72	113
Week 36	141	114	183
Week 48	225	184	309
Week 72	393	310	477
Week 96	561	478	645
Week 120	729	646	≥ 729

* For subjects who did not enter LTE phase, upper limit is “>= 113”; for subjects enrolled under PA1 who stayed in Main Study beyond Week 16, upper limit is 127.

The analysis windows for PASI including BSA, mNAPSI, SPARCC Enthesitis Index and LEI, LDI data are provided in [Table 3-4](#):

Table 3-4. Analysis Visit Windows for PASI including BSA, mNAPSI, SPARCC Enthesitis Index and LEI, LDI Data

Analysis Visit	Nominal Study Day	Visit Window Study Day	
		Lower Limit	Upper Limit
Baseline	1	(none)	1
Week 4	29	2	43
Week 8	57	44	71
Week 12	85	72	99
Week 16	113	100	Week 16 Visit Date – Study Day 1 + 1*
Analysis Visit	Nominal LTE Study Day	LTE Lower Limit	LTE Upper Limit
Week 20	29	2	43
Week 24	57	44	71
Week 28	85	72	113
Week 36	141	114	183
Week 48	225	184	309
Week 72	393	310	477
Week 96	561	478	645
Week 120	729	646	≥ 729

* For subjects who did not enter LTE phase, upper limit is “>= 113”; for subjects enrolled under PA1 who stayed in Main Study beyond Week 16, upper limit is 127.

The analysis windows for FACIT-Fatigue, SF-36v2, PsAID-12 data are provided in [Table 3-5](#)

Table 3-5. Analysis Visit Windows for FACIT-Fatigue, SF-36v2, PsAID-12 Data

Analysis Visit	Nominal Study Day	Visit Window Study Day	
		Lower Limit	Upper Limit
Baseline	1	(none)	1
Week 4	29	2	71
Week 16	113	72	Week 16 Visit Date – Study Day 1 + 1*
Analysis Visit	Nominal LTE Study Day	LTE Lower Limit	LTE Upper Limit
Week 48	225	2	393
Week 96	561	394	645
Week 120	729	646	≥ 729

* For subjects who did not enter LTE phase, upper limit is “>= 113”; for subjects enrolled under PA1 who stayed in Main Study beyond Week 16, upper limit is 141.

Treatment Policy estimand is defined for efficacy analyses, and for efficacy measurements, the analysis visit windows will be applied to all available data observed on study.

While on Treatment estimand is defined for safety analysis, and for vital signs, weight, and laboratory data, the analysis visit windows will be applied to data collected during the on-treatment period. The on-treatment period is defined up to the last dose date of any study drug + 7 days.

The safety data collected in the post-treatment safety follow up period will also be summarized. The analysis window for the post-treatment follow-up period is defined as from (the last dose date of any study drug + 8 days) to (the last dose date of any study drug + 30 days). Data obtained after last dose date plus 30 days will be excluded from the summaries, but will still be included in the listing.

3.7.3. Selection of Non-Efficacy Data in the Event of Multiple Records in an Analysis Visit Window

Depending on the statistical analysis method, single values may be required for each analysis window. For example, change from baseline by visit usually requires a single value, whereas a time-to-event analysis would not require 1 value per analysis window.

If multiple valid, nonmissing measurements exist in an analysis window, records will be chosen based on the following rules if a single value is needed:

- For baseline, the last nonmissing value on or prior to the first dosing date of study drug will be selected, unless specified differently. If there are multiple records with the same time or no time recorded on the same day, the baseline value will be the average of the measurements for continuous data, or the measurement with the lowest severity (e.g., normal will be selected over abnormal) for categorical data.
- For postbaseline values:
 - The record closest to the nominal day for that visit will be selected.
 - If there are 2 records that are equidistant from the nominal day, the later record will be selected.
 - If there is more than 1 record on the selected day, the average will be taken for continuous data and the worse severity will be taken for categorical data, unless otherwise specified.

4. SUBJECT DISPOSITION

4.1. Subject Enrollment and Disposition

A summary of subject enrollment will be provided by treatment group and overall for each country within each geographic region and investigator within a country. The summary will present the number and percentage of subjects enrolled. For each column, the denominator for the percentage calculation will be the total number of subjects analyzed for that column.

A similar enrollment table will be provided by randomization stratum. The denominator for the percentage of subjects in the stratum will be the total number of enrolled subjects. If there are discrepancies in the value used for stratification assignment between the IXRS and the clinical database, the value collected in the clinical database will be used for the summary. A listing of subjects with discrepancies in the value used for stratification assignment between the IXRS and the clinical database at the time of data finalization will be provided.

The randomization schedule used for the study will be provided as an appendix to the CSR.

A summary of subject disposition will be provided by treatment group and study phase (Main Study and LTE). This summary will present the number of subjects screened, the number of subjects who met all eligibility criteria but were not randomized with reasons subjects not randomized, the number of subjects randomized, and the number of subjects in each of the categories listed below:

- Safety Analysis Set
- Full Analysis Set
- Completed study drug (Main Study phase)
- Did not complete study drug with reasons for premature discontinuation of study drug (Main Study phase)
- Entered LTE phase
- Did not complete study drug with reasons for premature discontinuation of study drug (LTE phase)
- Did not complete the study with reasons for premature discontinuation of study in Main Study and LTE phase respectively

For the status of study drug and study completion and reasons for premature discontinuation, the number and percentage of subjects in each category will be provided. The denominator for the percentage calculation will be the total number of subjects in the Safety Analysis Set corresponding to that column.

The following by-subject listings will be provided by subject ID number in ascending order to support the above summary tables:

- Reasons for premature study drug or study discontinuation
- Reasons for screen failure (will be provided by screening ID number in ascending order)
- Lot number and kit ID of assigned study drugs

4.2. Extent of Study Drug Exposure and Adherence

Extent of exposure to study drug will be examined by assessing the total duration of exposure to study drug for Main Study and the level of adherence relative to the study drug for Main Study specified in the protocol.

4.2.1. Duration of Exposure to Study Drug

Total duration of exposure to any study drug for Main Study will be defined as last dosing date of any study drug for Main Study minus first dosing date of any study drug plus 1, regardless of any temporary interruptions in study drug administration, and will be expressed in weeks using up to 1 decimal place (e.g., 4.5 weeks).

For subjects with a partial last dosing date (ie, month and year of last dose are known), the latest of the dispensing dates of study drug bottles, study drug start dates and end dates, and the imputed last dose date (day imputed as 15) will be used as the final imputed last dose date. If the subject died and the death date is complete (i.e., not partial date) and before the imputed last dose date, the complete death date will be used as the imputed last dose date.

If only year is recorded (ie, month and day of last dose are missing), the latest of the dispensing month of study drug bottles, study drug start month, and study drug end month will be used to impute the unknown last dose month. If the subject died and the death date has month and year available and before the imputed last dose month, then the month of death will be used instead. With the month imputed, the aforementioned method will be used to impute the last dose date.

The total duration of exposure to any study drug for Main Study will be summarized using descriptive statistics and using the number (i.e., cumulative counts) and percentage of subjects exposed through the following time periods: Baseline (Day 1), Week 2 (Day 15), Week 4 (Day 29), Week 8 (Day 57), Week 12 (Day 85), Week 16 (Day 113). Summaries will be provided by treatment group for the Safety Analysis Set.

No formal statistical testing is planned.

4.2.2. Adherence to Study Drug

Adherence will be calculated separately for individual study drugs, including filgotinib 200 mg/PTM (tablets), filgotinib 100 mg/PTM (tablets), and adalimumab/PTM (syringes).

The total number of tablets or syringe administered will be summarized using descriptive statistics.

The presumed total number of tablets or syringes administered to a subject will be determined by the data collected on the drug accountability CRF using the following formula:

$$\begin{aligned} \text{Total Number of Tablets Administered} &= \\ & \left(\sum \text{No. of Tablets Dispensed} \right) - \left(\sum \text{No. of Tablets Returned} \right) \\ \text{Total Number of Syringes Administered} &= \\ & \left(\sum \text{No. of Syringes Dispensed} \right) - \left(\sum \text{No. of Syringes Returned} \right) \end{aligned}$$

If a bottle or a packaging kit is dispensed and the bottle or packaging kit is returned empty, then the number of tablets/syringes returned will be entered as zero. If a bottle or a packaging kit is dispensed but not returned (missing), then the number of tablets/syringes administered will be counted as zero.

On-Treatment Adherence will be calculated to assess the level of adherence to study drugs.

The level of on-treatment adherence to the study drug will be determined by the total amount of study drug administered relative to the total amount of study drug expected to be administered during a subject's actual on-treatment period based on the study drug regimen.

The level of on-treatment adherence will be expressed as a percentage using the following formula:

$$\text{On-Treatment Adherence (\%)} = \left(\frac{\text{Total Amount of Study Drug Administered}}{\text{Study Drug Expected to be Administered on Treatment}} \right) \times 100$$

Study drug expected to be administered for filgotinib 200 mg/PTM (tablets) = 1 × total duration of exposure to any study drug for Main Study (days).

Study drug expected to be administered for filgotinib 100 mg/PTM (tablets) = 1 × total duration of exposure to any study drug for Main Study (days).

Study drug expected to be administered for adalimumab/PTM (syringes) = $1 \times \text{ceil}[(\text{min}(\text{Last dose date of any study drug for Main Study, First dose date of any study drug} + 14 \times 7) - \text{First dose date of any study drug} + 1) / 14]$.

Descriptive statistics for the level of on-treatment adherence with the number and percentage of subjects belonging to adherence categories (e.g., $\{< 80\%, \geq 80 \text{ to } < 90\%, \geq 90\%\}$) will be provided by treatment group for the Safety Analysis Set.

No formal statistical testing is planned.

A by-subject listing of study drug administration and drug accountability will be provided separately by subject ID number (in ascending order) and visit (in chronological order).

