5.2.2. Packaging and Labeling of Filgotinib and PTM Filgotinib

Filgotinib tablets, 100 mg and 200 mg, and PTM filgotinib tablets, 100 mg and 200 mg, are packaged in white, high density polyethylene (HDPE) bottles. Each bottle contains 30 tablets, silica gel desiccant and polyester packing material. Each bottle is enclosed with a white, continuous thread, child-resistant polypropylene screw cap fitted with an induction-sealed, aluminum-faced liner.

Sufficient quantities of filgotinib tablets, 100 mg and 200 mg, and PTM filgotinib tablets to complete the entire study will be shipped to the investigator or qualified designee from the Gilead Supply Management Team (or its designee).

Study drugs to be distributed to participating sites shall be labeled to meet applicable requirements of the U.S. FDA, the EU Guideline to Good Manufacturing Practice – Annex 13 (Investigational Medicinal Products), the Ministerial Ordinance on Good Clinical Practice for Drugs in Japan, and / or other local regulations, as applicable.

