4.4. Assessment of COVID-19 Impact

This study was ongoing during the novel coronavirus (2019 nCoV [COVID-19]) pandemic which has caused a disruption in the regular visit schedules for this study. Some subjects were unable to attend onsite visits due to shelter in place guidelines, site closures, or other reasons. This section provides how special situations due to COVID-19 will be handled in the analysis.

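### The adherence rule scores an unreturned bottle or kit as no doses taken but still expects those doses, so a fully adherent completer missing one regularly used 4-week bottle is reported at about 75%

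*SAP*

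**What the plan says.** SAP 4.2.2 calculates adherence separately for the two tablet strengths and the syringes. The numerator is units dispensed minus units returned. Two special cases are defined. For a container returned empty, "then the number of tablets/syringes returned will be entered as zero", so everything dispensed counts as taken. For a container not returned at all, "then the number of tablets/syringes administered will be counted as zero".

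The tablet denominator is one per day of Main Study exposure. SAP 4.2.1 defines that exposure as last dose date minus first dose date plus one, "regardless of any temporary interruptions in study drug administration". The syringe denominator is also computed from dates alone. Neither section removes the period covered by an unreturned container, sets adherence to missing, or adds a second estimate.

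The planned output is "Descriptive statistics for the level of on-treatment adherence with the number and percentage of subjects belonging to adherence categories", with <80%, 80 to <90% and ≥90% offered as example bands. Total units administered are also summarised. A by-subject listing of administration and accountability is planned.

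**The concern.** A container that does not come back carries no information about how many doses were taken from it. The SAP turns that missing count into a zero in the numerator and leaves the matching doses in the denominator. Two subjects with identical dosing then get very different results: the one who hands back an empty bottle is credited with all of it, and the one who does not is credited with none. The dosing record may place both on drug throughout.

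What is at stake is the meaning of the adherence table. It is presented as drug taken relative to drug expected on treatment, but in part it measures drug-return logistics. The total-doses-administered summary has the same shortfall.

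**Working it through.** The documents state no adherence figure to reproduce, so the check applies the SAP 4.2.2 formula directly.

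**Inputs**
- Bottle size: "Each bottle contains 30 tablets, silica gel desiccant and polyester packing material" (Protocol 5.2.2).
- Dispensing: Day 1, Week 2 (floater supply), then Weeks 4, 8, 12 and 16 (Protocol Appendix 2). One bottle per strength per 4-week interval, hence 28 doses taken from each, is an assumption drawn from bottle size and visit spacing.
- Main Study length: Week 16 is Day 113 (SAP 4.2.1).
- Syringe kit size is not stated; one and two are both tried.

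**Tablets.** Let D be days of exposure and m the doses actually taken from the unreturned bottle. A fully adherent subject took D tablets. Reported adherence = 100 × (D − m)/D.

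| Fully adherent subject, one bottle unreturned | D | m | Reported |
|---|---|---|---|
| Completer, regular bottle | 113 | 28 | 85/113 = 75.2% |
| Exactly 16 weeks, regular bottle | 112 | 28 | 84/112 = 75.0% |
| As above, all 30 tablets taken from it | 112 | 30 | 82/112 = 73.2% |
| Stops at Day 84, regular bottle | 84 | 28 | 56/84 = 66.7% |
| Stops at Day 56, regular bottle | 56 | 28 | 28/56 = 50.0% |
| Stops at Day 28, only bottle | 28 | 28 | 0/28 = 0% |
| Stops at Day 100, last bottle (Days 85–100) | 100 | 16 | 84/100 = 84.0% |
| Floater, 14 doses taken from it | 112 | 14 | 98/112 = 87.5% |
| Floater, unused | 112 | 0 | 112/112 = 100% |

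**When the result is below 80%.** (D − m)/D < 0.80 requires m > 0.2 × D. At 112 days that is m > 22.4. A lost 28-dose bottle reaches 80% only when D ≥ 28/0.2 = 140 days, which is 27 days past the nominal Week 16 day. Even at Day 127, the upper Week 16 limit in SAP Table 3-1 for subjects who stayed on under Amendment 1, the figure is 99/127 = 78.0%.

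**Syringes.** Expected for a completer = ceil((98 + 1)/14) = 8. An unreturned one-syringe kit gives 7/8 = 87.5%; a two-syringe kit gives 6/8 = 75.0%.

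**Direction.** Since m cannot be negative, (D − m)/D never exceeds the true value. The rule cannot overstate adherence.

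**Alternatives for the completer with one regular bottle unreturned.** Counting that bottle as fully used gives (85 + 30)/113 = 101.8%, so a cap at 100% is needed. Removing its 28 days from both sides gives 85/85 = 100%.

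**The case against.** The strongest defence is that the rule is explicit and conservative: failure to return drug may itself go with failure to take it, so crediting nothing avoids flattering the result. That stands as a reason to keep the zero-count figure, but as a labelled lower bound. The SAP presents it as the only estimate.

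Four stronger readings are tempting, and the documents do not support them.

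- A reader might infer that any unreturned container puts an adherent subject below 80%. The floater, partly used last bottle and one-syringe cases above show otherwise.
- A reader might infer that unreturned bottles were common. SAP 4.4 says "Some subjects were unable to attend onsite visits due to shelter in place guidelines, site closures, or other reasons", and SAP 1.3 reports sponsor termination after 67 subjects. Both make non-return plausible, but neither gives a rate. A bottle not handed in at one visit may come back at the next. Protocol 5.5 requires return of all drug, and 5.5.1 provides for monitor verification.
- A reader might infer damage to the efficacy conclusions or a bias between arms. No analysis set uses adherence, the efficacy estimand includes data after drug discontinuation, no test is planned on adherence, and every arm handles the same three products under the same rule.
- A reader might infer that adherence is the only evidence of exposure because no pharmacokinetic analysis is visible. Parts of both documents are redacted, and dose dates come from the administration record, independently of bottle return.

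The accountability listing also lets a reader check individual subjects. It does not correct the summary table.

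**Conclusion.** The point holds as a minor one. SAP 4.2.2 converts an unknown count into complete non-adherence, and the error runs in one direction. For a fully adherent 16-week subject with one regularly used 4-week bottle unreturned, reported adherence is about 75% instead of 100%, and the shortfall grows with shorter exposure. This rests on one bottle per strength per 4-week interval with 28 doses taken from it.

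The effect is limited to descriptive summaries, and the actual number of affected subjects is unknown and could be nil. If any exist, the small groups make each one visible. Splitting 67 subjects 2:2:1:2 gives about 67 × 2/7 = 19 per filgotinib or placebo group and 67/7 = 10 on adalimumab (actual sizes are not given). One subject placed in the wrong band then shifts a percentage by about 1/19 = 5 points, or 1/10 = 10 points.

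**What to change.** In SAP 4.2.2:

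1. Label the zero-count result a lower bound.
2. Show beside it an upper bound that counts unreturned supply as taken, capped at 100%.
3. Report, by treatment group and product, the number of subjects with any unreturned bottle or kit.

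If a single estimate is wanted, either restrict it to subjects with complete accountability, or exclude the unaccounted interval from both numerator and denominator with a stated rule for floater supply. The exclusion should not be the main presentation. It assumes that unaccounted days resemble accounted ones, and the interval is not well defined for floater bottles or for 30-tablet bottles covering 28 days.

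The accountability data are already collected. The cost is some SAP wording, modest programming and a slightly longer adherence table. If the SAP is final, SAP Section 1 already provides for documenting such a change in the clinical study report.
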